Both the frequency of WP use and the manner with which it is smoked contributes to the development and maintenance of nicotine dependence.⁹⁻¹¹ WP smoking delivers pharmacologically active doses of nicotine to the user.^{12,13} Although most WP smokers in the U.S. smoke WP intermittently, some eventually move on to more frequent use.^{14,15} **If flavorings are determined to influence users to initially try WP, improve their perceived satisfaction from use of the product, and/or make it more palatable to puff more frequently or take longer/deeper puffs, then they would be contributing to the initiation and maintenance of WP dependence.** Moreover, current level of WP dependence may moderate the impact of flavorings on smoking patterns. Unflavored WP tobacco is more difficult to find and purchase, and internet customer reviews suggest that few WP users try and even fewer continue to use unflavored tobacco (“didn’t taste good”, “may be a little hard for less experienced smokers”); however, some product reviews from WP aficionados are more positive (“This is a blend to be sipped and enjoyed slowly”), suggesting that current WP dependence level may be an important factor in the role of flavors.¹⁶

The overall aim of the current study is to determine if flavorings contribute to the initiation and maintenance (i.e., abuse liability) of WP smoking and also influence how a WP is smoked (i.e., smoking topography), which has implications for both risk of dependence but also smokers’ level of exposure to tobacco-related toxicants. Using a randomized crossover-design, 76 current WP smokers (38 low dependent, 38 high dependent) will complete four counterbalanced WP smoking sessions (preferred flavored-sweetened, preferred flavored-very low sweetened, unflavored-sweetened, unflavored-very low sweetened) that are preceded by 12 hours of tobacco/nicotine abstinence. Sessions will be separated by a standard 48-hour washout period.

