Aim 1: To understand how flavorings impacts WP initiation, smoking behaviors, abuse liability, and exposure to tobacco-related toxicants. (H1a) *Flavored-sweetened WP tobacco will be associated with longer and more frequent puffing resulting in the greatest overall levels of smoke inhalation (mL of smoke inhaled), (H1b) highest abuse potential, and (H1c) greatest levels of exposure to nicotine and carbon monoxide (CO), followed by unflavored-sweetened WP, then flavored-very low sweetened and lastly unflavored-very low sweetened WP.* (H1d) *A majority of WP smokers will report having initiated WP smoking with flavoredsweetened tobacco and report flavoring as an important reason for trying WP.*

Aim 2: To understand whether level of WP dependence influences the impact of WP flavoring on smoking behaviors, intentions for continued use, abuse liability, and exposure to tobacco-related toxicants. Compared to high dependence users smoking unflavored WP tobacco, low dependence users will show greater declines in (H2a) puff frequency and duration resulting in lower levels of smoke inhalation, (H2b) intentions of continued use, (H2c) abuse liability, and (H2d) their exposure to nicotine and CO while smoking unflavored-sweetened and unflavored-unsweetened (greatest decline) vs. flavored-sweetened WP tobacco.

[figure not shown]

Our team is uniquely suited to conduct this investigation. Understanding how WP smokers and smoking would be influenced by a flavoring ban is critically important. This novel study addresses seven of the FDA's research priorities and will contribute knowledge urgently needed by the FDA and health officials to effectively regulate WP tobacco in a way that best serves public health.

SIGNIFICANCE

The rapidly growing popularity of WP smoking: While traditional tobacco product use (cigarettes, cigars, etc.) continues to decline, WP smoking is on the rise in the United States.^{1,17} From 2011 to 2014, current (past 30-day) cigarette use declined from 15.8% to 9.2% among high school students, while during the same period, current WP use increased from 4.1% to 9.4%.¹ Additionally, WP has overtaken cigarettes as the most frequently tried tobacco product among young adults (46.6%)¹⁸ and is frequently the first tobacco product ever tried (12.0%).² Recent estimates of current and ever WP use among adults also indicates an upward trend, with current and ever use rates currently at their highest (1.5% and 9.8%, respectively).¹⁹

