The extant WP research indicates that flavors have played a significant role in the spread of WP smoking.⁴⁷ In a nationally representative sample, 59% of WP smokers reported use of flavored tobacco, more than any other tobacco product.⁴³ Participants in qualitative research emphasize the importance of flavors in WP smoking stating, "I think it has to do with the flavor that got me to smoke it. It was a lot of variety" and "I like it, it was flavored and it was fun after a while".⁴⁸ Individuals also cite flavors as giving the impression that WP smoking in general is relatively harmless,⁴⁸ and that flavored WP tobacco is "healthier" than unflavored WP tobacco.⁴⁹ Anecdotal evidence of the importance of flavors in WP can be found in online reviews. Consumers indicate the significance of flavors in their reviews of unflavored shisha and state, "it was too strong" and "didn't taste good." One established user stated, "It is not for the new smokers," indicating the role of flavors in the initiation of WP smoking among naïve users. Making matters worse, emerging evidence indicates that WP use not only increases smokers' intentions and interest in using cigarettes,^{50,51} but longitudinal and prospective research shows that WP may also act as a gateway product to regular cigarette use.⁵²⁻⁵⁴ For these reasons, researchers and health officials have begun calling for a ban on flavored WP tobacco.³

Humectants, like glycerine, act as sweeteners and may enhance WP tobacco flavors. Regulators have limited the amount of glycerin (≤5%) in WP tobacco sold in Germany; substantially less than the levels sold in the U.S. (~25-50%).^{85,86} Unfortunately, Germany has not regulated the separate sale of bottles of WP-specific glycerin additive which are now sold alongside WP tobacco on German WP websites. The sale of these bottles

indicates the importance of glycerin to WP tobacco users. Thankfully, if the present study's hypotheses are supported, the Tobacco Control Act grants the FDA regulatory authority over these component products.

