Design Overview: [name] and his team will conduct a randomized crossover-design clinical laboratory trial at the Oklahoma Tobacco Research Center. WP smokers will complete four (preferred flavored sweetened, unflavored-sweetened, preferred flavored-very low sweetened, unflavored-very low sweetened), 2hr long counterbalanced WP smoking sessions that are preceded by 12 hours of overnight tobacco abstinence, biochemically verified by exhaled carbon monoxide (eCO<20ppm). Sessions will take place in a separately ventilated experimental smoking room within the OTRC and will be separated by a standard 48-hour washout period. Due to the variability in nicotine content between different brands and flavors of WP tobacco,⁶² nicotine levels will be tested prior to study recruitment by [name] to ensure the same level of nicotine between WP tobacco. Outcome measures will include smoking behavior, toxicant exposure, and subjective effects.

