a specified interval (e.g. 1.5 +/- 0.2 lpm at 5 cm H₂O) will be retained for the study. This will assure that WPs used throughout the study are research qualified, while constructed of materials typical of what is used in the natural environment. All aspects of the WP apparatus will be held constant (water level, type of foil, disposable mouthpieces, and hoses). In every session, the waterpipe hose will be tipped with a new, sterile, disposable mouthpiece. Participants accompanying the index participant, will smoke from a second Mya Saray WP.

Charcoal: We will use self-lighting charcoal briquettes. Each piece of charcoal will be pre-weighed and will be placed on top of the foil. Tobacco: For the flavored-sweetened WP smoking session, participants will be able to choose their preferred flavor from a selection of the most popular Nakhla brand flavors that we will keep on hand to ensure availability. For the unflavored-sweetened session, participants will be provided Nakhla Zaghloul and for the flavored-very low sweetened and unflavored-very low sweetened session, the German version of Nakhla Shisha. Nakhla was chosen because it is a popular brand and is one of the few that has a flavored, unflavored-sweetened, flavored-very low sweetened and unflavored-very low sweetened tobacco product.

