Power and Data Analytic Plan: Power - Aim 1 (assumes 20% attrition of 82 participants recruited): Overall levels of smoke inhalation is our primary outcome; thus, we will estimate power based on this outcome. As no study to date has investigated the impact of WP flavoring, assumptions are based on a clinical laboratory investigation of percent changes in smokers' topography while smoking menthol vs. non-menthol cigarettes.⁷⁷ According to Chow et al.,⁷⁶ 60 WP users in a Williams 6×4 crossover design achieve >87.5% power to detect a decrease of ≥23L (or ≥20% decrease for unflavored-very low sweetened vs. flavored-sweetened) and ≥18L (unflavored-very low sweetened vs. unflavored-sweetened) in total volume of smoke inhaled using two-sided tests with 0.025 alpha level (used to adjust for the aforementioned 2 pairwise comparisons), conservatively assuming a mean total volume of 115L, 110L, 100L, and 92L for flavored-sweetened, unflavored-sweetened, flavored-very low sweetened, and unflavored-very low sweetened condition, respectively, a common standard deviation of 30L, and a within-subject correlation varying from 0.1 to 0.8. Power - Aim 2: Based on a comparison study of puff topography between high vs. low dependent WP smokers,⁶³ we assume a decrease of 10L (unflavored-very low sweetened vs. flavored-sweetened) and 5L (unflavored-very low sweetened vs. unflavored-sweetened) in total volume of smoke inhaled among high dependence WP users, and a decrease of 44L (or 40% decrease for unflavored-very low sweetened vs. flavored-sweetened) and 39L (unflavored-very low sweetened vs. unflavored-sweetened) in total volume of smoke inhaled among low dependence WP users. As in the power calculation for Aim 1, we assume a common standard deviation of 30L in total volume and a within-subject correlation varying from 0.1 to 0.8. Based on these assumptions, we estimate that 30 high dependence and 30 low dependence WP users achieve >83% power to detect the difference between high and low dependence groups in terms of Δ total volume (unflavored-very low sweetened vs. flavored-sweetened or unflavored-very low sweetened vs. unflavored-sweetened), using a two-sided, two-sample t-test with an adjusted alpha level of 0.025.

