Data Analytic Plan: Data will be summarized using mean (SD). Both overall and stratified (by dependence level) statistics will be reported. For Aim 1, we will use linear mixed effects models (with a random subject effect) to assess the main effect of flavor on total volume of smoke inhaled, abuse liability score, nicotine and CO exposure levels. In addition, period and carryover effects will be considered in the model. All pairwise comparisons for the main effect of flavor will be conducted and Bonferroni-adjusted p-values reported. For Aim 2, we will further include dependence level (high vs. low) and its interaction with flavoring in the linear mixed effects models (as in Aim 1) for outcomes including total volume of smoke inhaled, interest in continued WP use, abuse liability score, and nicotine and CO exposure levels. If the interaction term is significant, flavoring group differences in the outcome for high and low dependence subjects will be compared using contrasts, again adjusting for multiple comparisons with Bonferroni's method. Data will be transformed as appropriate. Missing data will not be imputed and likelihood based linear mixed models will yield valid statistical inference under missing at random (MAR) and ignorable missing mechanism assumptions. A two-sided p-value of <0.05 defines statistical significance. The SAS software (v9.3, Cary, NC) will be used for all data analyses.

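### The four conditions form a within-subject 2×2, but no marginal flavor or sweetener contrast is prespecified, and neither powered comparison isolates flavor (cheap improvement)

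*Combined protocol and SAP*

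**What the plan says.** Specific Aims lists the sessions as "preferred flavored-sweetened, preferred flavored-very low sweetened, unflavored-sweetened, unflavored-very low sweetened", and every participant is to complete all four. Design Overview and WP Smoking Session Procedures repeat the list. This is a complete crossing of two two-level factors within each person.

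For Aim 1, the Data Analytic Plan fits a linear mixed model with a random subject effect and one treatment term, called the main effect of flavor. It continues: "All pairwise comparisons for the main effect of flavor will be conducted and Bonferroni-adjusted p-values reported". A two-level factor has only one pair, so the term is naturally read as a four-level condition factor with six tests at 0.05/6. The plan does not say so outright. The only interaction it names is dependence level by flavoring, for Aim 2.

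The Aim 1 power statement assumes "a mean total volume of 115L, 110L, 100L, and 92L" for flavored-sweetened, unflavored-sweetened, flavored-very low sweetened and unflavored-very low sweetened. The two differences that it powers are 23 L ("or ≥20% decrease for unflavored-very low sweetened vs. flavored-sweetened) and ≥18L (unflavored-very low sweetened vs. unflavored-sweetened").

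H1a to H1c predict an ordering: flavored-sweetened highest, "followed by unflavored-sweetened WP, then flavored-very low sweetened and lastly unflavored-very low sweetened WP".

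**The concern.** The overall aim is whether flavorings contribute to waterpipe smoking, and the Innovation section offers the data in support of a standard prohibiting flavoring. The Significance section treats glycerin sweetener separately and says of the bottled additive that "the Tobacco Control Act grants the FDA regulatory authority over these component products". A flavor effect and a sweetener effect therefore bear on different regulatory actions.

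Neither powered comparison isolates flavor. In one, both factors change; in the other, only sweetener does. If the 23 L pair is significant and neither flavor-only pair is, the planned tests do not show that flavor contributed. The design already contains a more precise flavor estimate, averaged over sweetener level, which the plan does not ask for. If it is added after the data are seen, it will be post hoc.

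**Working it through.** **Inputs** (Power – Aim 1, unless stated): means 115 / 110 / 100 / 92 L; SD 30 L; within-subject correlation rho 0.1 to 0.8; n = 60. The completer target of 76 is from Specific Aims and Participants. Alpha is 0.025 in the power statement and 0.05/6 = 0.0083 in the Data Analytic Plan.

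**Formulas.** Standard errors:
- pair: 30·√(2(1−rho)/n)
- marginal contrast: 30·√((1−rho)/n)
- interaction: 60·√((1−rho)/n)

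The ratio of marginal to pair is 1/√2 = 0.707, i.e. 29% smaller. Power is from the two-sided noncentral t with 3(n−1)−3 df (174 at n = 60, 222 at n = 76).

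**The plan's own figure.** 18 L, n = 60, rho 0.1, alpha 0.025: SE = 30·√(1.8/60) = 5.20 L and power is 88.4% (87.5% with 59 df). The plan states more than 87.5%, so its figure reproduces.

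**Contrasts implied by the planning means**
- Flavor: [(115−110)+(100−92)]/2 = 6.5 L
- Sweetener: [(115−100)+(110−92)]/2 = 16.5 L
- Interaction: (115−110)−(100−92) = −3 L

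These are assumptions of the plan, not evidence of what the trial will find.

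**Flavor under the current plan (0.05/6) and with a marginal test.** The rows for at least one pair and for the combined pair come from 1,000,000 simulations of the four condition means with a common estimated error variance.

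| | rho 0.1 | 0.5 | 0.8 |
|---|---|---|---|
| 115 vs 110 L, n = 60 | 5% | 9% | 27% |
| 100 vs 92 L, n = 60 | 13% | 28% | 72% |
| At least one of these, n = 60 | 17% | 34% | 80% |
| At least one of these, n = 76 | 23% | 44% | 90% |
| 115 vs 92 L significant, neither flavor-only pair significant, n = 60 | 79% | 66% | 20% |
| Marginal flavor at 0.025, n = 60 | 31% | 55% | 93% |
| Marginal flavor at 0.025, n = 76 | 40% | 66% | 97% |
| Marginal flavor at 0.05/6, n = 60 | 19% | 39% | 86% |
| Marginal flavor at 0.05/8 (one family with the six pairs), n = 60 | 16% | 35% | 84% |
| 115 vs 92 L significant (0.05/6), marginal flavor not (0.025), n = 60 | 65% | 45% | 7% |

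**Precision at n = 60.** The 95% CI half-width is 1.974 × SE:
- marginal: 1.974 × 3.674 / 2.739 / 1.732 = 7.3 / 5.4 / 3.4 L
- pair: 1.974 × 5.196 / 3.873 / 2.449 = 10.3 / 7.6 / 4.8 L
- interaction: 1.974 × 7.348 / 5.477 / 3.464 = 14.5 / 10.8 / 6.8 L

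**Product differences.** WP Materials has unflavored-sweetened participants "provided Nakhla Zaghloul and for the flavored-very low sweetened and unflavored-very low sweetened session, the German version of Nakhla Shisha"; flavored-sweetened is a chosen Nakhla flavor. Of the tobacco's properties, Design Overview matches only nicotine ("to ensure the same level of nicotine between WP tobacco"). Suppose that Zaghloul shifts its cell by d L for reasons other than flavor (size assumed; the documents give none). The marginal flavor contrast becomes 6.5 − d/2, the 115 vs 110 L pair becomes 5 − d, and the 100 vs 92 L pair stays at 8 L. For d = −5 / +5 the marginal contrast is 9.0 / 4.0 L and the first pair is 10 / 0 L.

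**The case against.** The strongest reply is that this is a preference for efficiency. H1 states an ordering of four products, and all-pairwise testing answers that. Two of the six pairs isolate flavor, and either one, if significant, supports attribution. All of this stands. A reader might infer that the planned analysis is invalid or cannot detect a flavor effect; the documents do not support that.

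The second reply concerns alpha. The move from 17 / 34 / 80% to 31 / 55 / 93% sets one test at 0.025 against two at 0.05/6. At 0.05/6 for every test, the marginal contrast has 19 / 39 / 86%. Under one 0.05 shared with the six pairs it has 16 / 35 / 84%, essentially no gain at rho 0.1 to 0.5. The comparator matters in the other direction too: if the two flavor-only pairs share 0.025 (0.0125 each), at least one is significant in 22 / 40 / 84% at n = 60. Pooling therefore contributes something, but the power gain is not free.

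Third, the 79 / 66 / 20% owes more to small assumed flavor effects than to the missing contrast. With the marginal test at 0.025, 65 / 45 / 7% remains. The Smoking Behavior Measure section calls topography highly stable, which favors higher rho, but gives no figure.

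Fourth, the marginal contrast averages a pair within one named product line with a pair that switches to Zaghloul. Making it confirmatory would also demote the only two comparisons that the sponsor powered. A reader might infer that the main effects must replace those pairs; for these reasons that does not follow.

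**Conclusion.** The point holds as a cheap improvement. The design is a 2×2, the public text prespecifies no marginal or interaction contrast, and neither powered comparison isolates flavor. On the planning means, with SD 30 L and n = 60, the planned tests show flavor through at least one pair in 17 / 34 / 80% of trials. The combined pair is significant without that in 79 / 66 / 20%.

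The firm gain is in estimation: a flavor estimate whose standard error is 29% smaller than any pair's, at any rho. A gain in power depends on how alpha is allocated. Even at 0.025, flavor power reaches 80% only from a rho of about 0.71 (n = 60) or 0.63 (n = 76).

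All power figures rest on the plan's means and common SD. They ignore the carryover terms that the Data Analytic Plan mentions and any clustering from the self-selected dyads, so they are idealized.

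**What to change.** 1. Keep the mixed model and the six Bonferroni-adjusted pairwise tests as planned.
2. Before the data are seen, prespecify from the same model the flavored-vs-unflavored and sweetened-vs-very-low-sweetened marginal contrasts, each with an estimate and 95% CI. Report the flavor-by-sweetener interaction as an estimate with 95% CI.
3. Describe flavored-sweetened vs unflavored-very low sweetened as a combined effect of flavor and sweetener.
4. Show the flavored vs unflavored very low sweetened pair beside the marginal flavor contrast, as it is the only flavor-only pair within one named product line.
5. If the sponsor chooses to test the marginal contrasts confirmatorily, state the alpha split and the flavor power that follows: 31 / 55 / 93% (n = 60) or 40 / 66 / 97% (n = 76) at 0.025 each, or 16 / 35 / 84% (n = 60) at 0.05/8.

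The cost is SAP wording; no participants, visits or measurements are added. The SAP should state the limits: the marginal flavor contrast averages over sweetener level and carries product differences, the interaction will be imprecise, and the power figures leave out carryover terms and dyad clustering.

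### Ordinary Bonferroni over the six Aim 1 pairwise comparisons is valid but needlessly conservative: Holm's step-down version gives the same error control and adds about 2 to 26 points of power on the adjacent steps

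*Combined protocol and SAP*

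**What the plan says.** The Data Analytic Plan, within the section Power and Data Analytic Plan, sets the Aim 1 rule: "All pairwise comparisons for the main effect of flavor will be conducted and Bonferroni-adjusted p-values reported". The overall level is given in the same paragraph: "A two-sided p-value of <0.05 defines statistical significance". For Aim 2, contrasts that follow a significant interaction are handled by "again adjusting for multiple comparisons with Bonferroni's method". No step-down procedure is named, no reason for plain Bonferroni is given, and no simultaneous confidence intervals are planned.

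Aim 1 in Specific Aims predicts a complete ranking of the four products. Flavored-sweetened comes first, "followed by unflavored-sweetened WP, then flavored-very low sweetened and lastly unflavored-very low sweetened WP".

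The power paragraph states that "60 WP users in a Williams 6×4 crossover design achieve >87.5% power" for two contrasts, 23 L and 18 L, "using two-sided tests with 0.025 alpha level (used to adjust for the aforementioned 2 pairwise comparisons"). Its inputs are given as "conservatively assuming a mean total volume of 115L, 110L, 100L, and 92L" and "a common standard deviation of 30L, and a within-subject correlation varying from 0.1 to 0.8". It states no power for any other pair.

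**The concern.** Single-step Bonferroni holds every comparison to the strictest threshold, however many of the others are clearly different. Holm applies that threshold only to the smallest p-value and relaxes it as hypotheses are rejected. The difference matters most when several true differences are expected, and this plan expects all six: H1 ranks the four products and the power paragraph assumes four distinct means.

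The smallest assumed differences are the adjacent steps of the ranking: 5 L, 10 L and 8 L. Two of them are the only comparisons that change flavor with the sweetener level held fixed:

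- flavored-sweetened against unflavored-sweetened (5 L);
- flavored-very low sweetened against unflavored-very low sweetened (8 L).

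Flavor is the trial's central question. The avoidable loss of power therefore includes the comparisons that answer it most directly.

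**Working it through.** **Inputs.** Means 115, 110, 100 and 92 L, SD 30 L, correlation ρ from 0.1 to 0.8, 60 users and alpha 0.025 come from the power paragraph. The 76 completers come from the Participants section. The overall two-sided 0.05 and the mixed model with a random subject effect come from the Data Analytic Plan.

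**Step 1: reproduce the plan's own figure.** For a within-subject contrast, SE = 30 × √(2(1 − ρ)/n). The least favorable case is ρ = 0.1. With n = 60, SE = 30 × √(1.8/60) = 5.196 L.

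- 18 L: 18/5.196 = 3.464. Power = Φ(3.464 − 2.241) = 88.9%. A paired t-test (59 df) gives 87.5% and a pooled-error t-test 88.5%.
- 23 L: 23/5.196 = 4.426. Power = Φ(4.426 − 2.241) = 98.6%.

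The stated power above 87.5% reproduces.

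**Step 2: thresholds.** Bonferroni tests all six pairs at 0.05/6 = 0.0083. Holm orders the p-values and compares them in turn with 0.05/6, 0.05/5, …, 0.05/1, stopping at the first failure. Any p-value at or below 0.05/6 is rejected by both.

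**Step 3: error control.** Simulated familywise error, Bonferroni and then Holm:

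- all four means equal: 0.041 and 0.041;
- three means equal: 0.023 and 0.044;
- two equal pairs: 0.017 and 0.049.

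Both stay within 0.05. Once some differences are real, Bonferroni leaves much of the allowance unused.

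**Step 4: power.** Simulation of the four-condition crossover with compound-symmetric errors: within-subject variance 900(1 − ρ), pooled error on 3(n − 1) − 3 df, 1,000,000 runs per setting. Entries are power in percent, Bonferroni → Holm.

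| n | ρ | 5 L | 10 L | 8 L | 15 L | 18 L | 23 L |
|---|---|---|---|---|---|---|---|
| 60 | 0.1 | 4.6 → 7.5 | 23.3 → 31.0 | 13.3 → 18.6 | 58.7 → 65.0 | 78.6 → 82.2 | 95.9 → 96.4 |
| 60 | 0.5 | 8.7 → 16.4 | 46.8 → 59.8 | 27.6 → 40.3 | 88.4 → 92.4 | 97.5 → 98.4 | 99.9 → 100 |
| 60 | 0.8 | 26.9 → 50.7 | 92.0 → 97.8 | 72.4 → 86.6 | 100 → 100 | 100 → 100 | 100 → 100 |
| 76 | 0.1 | 5.9 → 10.3 | 31.1 → 41.0 | 18.0 → 25.9 | 72.0 → 78.1 | 89.1 → 91.6 | 98.9 → 99.1 |
| 76 | 0.5 | 11.6 → 22.9 | 59.7 → 74.0 | 36.9 → 52.7 | 95.5 → 97.5 | 99.5 → 99.7 | 100 → 100 |
| 76 | 0.8 | 35.9 → 61.9 | 97.3 → 99.5 | 84.3 → 93.8 | 100 → 100 | 100 → 100 | 100 → 100 |

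The adjacent-step gains run from 2.2 points (10 L, n = 76, ρ = 0.8) to 25.9 points (5 L, same setting).

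**Step 5: check of the largest gain.** The most that Holm can give one contrast is the move from 0.05/6 to 0.05. For 5 L with n = 76 and ρ = 0.8, SE = 30 × √(0.4/76) = 2.176 L and 5/2.176 = 2.297. Then Φ(2.297 − 1.960) − Φ(2.297 − 2.638) = 63.2% − 36.7% = 26.5 points. This is essentially the maximum for any contrast.

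**Step 6: joint results, n = 76, Bonferroni → Holm.**

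- Both flavor-only steps declared: about 1% → 4% (ρ = 0.1), 4% → 15% (ρ = 0.5), 31% → 60% (ρ = 0.8).
- All three adjacent steps declared: below 0.1% → 0.5%, 0.4% → 9%, 28% → 59%.

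**The case against.** The strongest reply is that nothing here is wrong. Bonferroni controls the error rate, contradicts nothing else in the plan and comes with matching simultaneous intervals. The trial is sized on the 23 L and 18 L contrasts, and these gain little. The largest gain for either is 3.6 points (18 L, n = 60, ρ = 0.1), so no stated power depends on the change. All of this stands, and it makes the point one of efficiency, not validity.

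Three stronger readings are tempting, and the documents do not support them.

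- **That the adjacent steps in general lose some 26 points.** Only the 5 L step at ρ = 0.8 comes close, with 25.9 points at n = 76 and 23.8 at n = 60. At ρ = 0.1 the adjacent gains are about 3 to 8 points with 60 completers and 4 to 10 with 76.
- **That all three adjacent steps separate flavor from sweetener.** By the condition names, the 10 L step (unflavored-sweetened against flavored-very low sweetened) changes both. Only the 5 L and 8 L steps isolate flavor. The pairs that isolate sweetener are not adjacent (15 L and 18 L) and gain at most about 6 points.
- **That Holm would let the trial demonstrate the H1 ranking.** Step 6 of the working shows that it would not at low or middle correlation.

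Two limits on the evidence also stand. The simulation leaves out carryover and the self-selected dyads, so the exact gains are approximate. No gain has been computed for the Aim 2 contrasts, whose number the plan does not list.

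**Conclusion.** The point holds as a cheap improvement. The plan's wording is read as single-step Bonferroni, since nothing in it suggests a step-down version. That choice is valid but gives up power for no stated reason. The gain from Holm depends on the step, the number of completers and the correlation, and it matters most for the two flavor-only comparisons. These sizes rest on the plan's assumed means, SD and correlation range, with compound symmetry and complete data. That Holm never loses a Bonferroni rejection, and controls the same familywise error, does not depend on those assumptions.

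The power paragraph adjusts for two comparisons while the analysis adjusts for six. That mismatch is a separate matter, which Holm only partly eases: at n = 60 and ρ = 0.1 the 18 L contrast has 82.2% power with Holm, still below the stated 87.5%.

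**What to change.** In the Data Analytic Plan, replace the Bonferroni adjustment of the Aim 1 pairwise p-values with *Holm (step-down Bonferroni) adjusted p-values*, before the data are analyzed. The same wording can be used for the Aim 2 contrasts. Holm can only help there, though the size of the benefit is not known.

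The cost is one line of text, with no new data, participants or procedures. The one downside is that Holm has no simple matching simultaneous confidence intervals. If intervals are wanted, report Bonferroni intervals alongside and say that they may be wider than the Holm decisions imply.
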